6.4 STUDY INTERVENTION COMPLIANCE

Each dose of study product will be administered by hospital nursing staff to randomized participants while they are in the hospital. Study drug administration will be documented in the site medication administration record or research record according to local procedures. A compliance log will be maintained in the eCRF containing participant ID, bottle number and batch number, route, and date and time of administration. Problems with participant medication adherence during hospitalization is not anticipated as the medications will be managed by hospital nursing staff. Upon discharge, if this occurs before 10 days of hospitalization, participants will receive study drug for the remaining days to complete a total duration of 10 days. These participants will receive verbal and written instructions on administering study drug. Participants will be asked to keep a written log as to when they self-administered study drug with dates and times recorded. If a care provider (i.e., family member) is present in the participant's home, daily pill counts will also be performed during the virtual phone or video visit.

6.5 CONCOMITANT THERAPY

All standardized treatment and management for any comorbidity and concomitant condition are permitted. Concomitant therapy with niacin, nicotinamide, NR and their derivatives are prohibited during the duration of the study.

6.5.1 RESCUE MEDICINE

To our knowledge there is no specific rescue medicine for NR as there is no known toxicity associated with this compound. If a rescue medicine is being considered for a participant for underlying COVID-19 or other intercurrent illness, this may be a reason that warrants stopping study drug. Any such decision will be made by the primary care team and the participant and the study team will be informed.

7 STUDY INTERVENTION DISCONTINUATION AND PARTICIPANT DISCONTINUATION/WITHDRAWAL

7.1 DISCONTINUATION OF STUDY INTERVENTION

Discontinuation from study intervention does not mean discontinuation from the study (i.e., withdrawal of consent), and remaining study procedures will be completed as indicated by the study protocol. Randomized participants who wish to discontinue study medications will be encouraged by the site PI and study coordinator to continue with the visits, laboratory tests, and data collection so data will be available for intent to treat analysis of the trial. The site PI will encourage passive data collection such as hospitalization documentation and EHR for participants who no longer want to attend visits.

7.2 PARTICIPANT DISCONTINUATION/WITHDRAWAL FROM THE STUDY

Participants are free to withdraw from participation in the study at any time upon request, for any reason, and without any consequence. Participants should be listed as having withdrawn consent only when they no longer wish to participate in the study and no longer authorize the investigators to make efforts to continue to obtain data. A participant has a right to withdraw from the current study and enroll in a different research study at any time point. However, participants will remain in the current study and all data will be collected as per the Schedule of Activities (section 1.3), Table 1 unless participants withdraw consent.

The study investigators have the right to discontinue the study drug at any time, which may be due but not limited to the following reasons:

- For an individual participant, a suspected drug-related event of hypersensitivity Grade 2 or higher;
- The investigator believes that for safety (e.g., SAE) or tolerability reasons it is essential for the participant to stop treatment;
- The investigator formally unblinds the participant's treatment allocation for safety reasons;
- The participant requires renal replacement therapy or dialysis of any type (Note: The requirement for dialysis is the only endpoint for which treatment with double-blind study drug should be discontinued;
- The participant takes prohibited NR supplements (multivitamins are allowed);
- Newly reported results of parallel clinical studies and/or animal studies indicating toxicity, teratogenicity, carcinogenicity or reproduction toxicity of NR at similar doses administered in this study;

Participants who are permanently discontinued from receiving investigational product will be followed for protocol-specified assessments unless consent is withdrawn from further study participation, or the participant is lost to follow-up.

In the event of a study drug discontinuation due to safety and tolerability, participants will continue to receive available and/or standard management for COVID-19 and comorbidities as

clinically indicated. Participants who discontinue study drug will continue subsequent study visit procedures (including biosample collections) to assess safety and worsening or progression of any health issues that might be attributable or plausibly related to study drug. As the study is an intent to treat analysis, all participant data will be obtained and processed in the same manner regardless of study drug discontinuation for any reason.

The reason for participant discontinuation or withdrawal from the study will be recorded on the REDCap eCRF. Withdrawal of consent prior to receipt of study drug will constitute a screen-failure and will be recorded. Participants who sign the informed consent form and are randomized but do not receive the study intervention may be replaced. Participants who sign the informed consent form, and are randomized and receive the study intervention, and subsequently withdraw, or are withdrawn or discontinued from the study, will not be replaced.

Data recorded up to the point of withdrawal will be included in the trial analysis, unless consent to use data has also been withdrawn. Withdrawal of consent after randomization and administration of one or more doses of study drug will lead to discontinuation of study interventions but study site will request access to EHR for data related to the trial.

Criteria for Stopping Study Drug

Administration of the blinded study drug may be stopped temporarily or permanently for (1) adverse events, (2) clinical deterioration, or (3) evidence of an alternative cause to the participant's symptoms. Study intervention will also be discontinued permanently when a participant:

- a) receives dialysis treatment for the management of AKI;
- b) develops thrombocytopenia defined as <75,000/microL in blood platelet count;
- c) is found to have abnormal liver function test (AST, ALT, total bilirubin, or alkaline phosphatase) >4 times the upper limit of normal without other identifiable cause;
- d) is found to have abnormal serum CPK levels >4 times the upper limit of normal without other identifiable cause.

If a participant experiences an AE that the patient (or LAR), the treating clinicians, or investigators feel merits temporarily or permanently stopping the study drug, the study drug will be stopped. The explanation for stopping the study drug will be recorded in the REDCap eCRF, and the AE will be recorded and reported according to the AE reporting guidelines. Participants will stop study drug, but data collection will continue as usual.

7.3 LOST TO FOLLOW-UP

The following actions will be taken if a participant is not able to be contacted or fails to return to the clinic for the required follow-up study visits:

Nicotinamide Riboside for AKI in COVID-19 positive inpatients Protocol #: Not yet assigned

- The study team will attempt to contact the participant and/or relative(s) in file and to reschedule the missed visit as soon as participant is available after the protocol-specific time window or perform a remote phone visit at the least.
- Before a participant is deemed lost to follow-up, a study team member will make every effort to regain contact with the participant and/or relative(s) in file (where possible, 3 telephone calls and, if necessary, a certified letter to the participant's last known mailing address or local equivalent methods).

Should the participant continue to be unreachable, EHR will be reviewed to document participant's vital status, and he or she will be considered to have withdrawn from the study with a primary reason of lost to follow-up.

8 STUDY ASSESSMENTS AND PROCEDURES

8.1 EFFICACY ASSESSMENTS

Given the infectious risk from COVID-19 and potential shortages of PPE, we will minimize face-to-face contact between participants and non-clinical staff. Additionally, minimizing research activities and conducting the trial in a pragmatic manner will increase the ability to complete the trial in the face of strained clinical and research resources during the COVID-19 pandemic. We will emphasize data that can be collected from the EHR, laboratory values as part of routine clinical care, and assessments that can be completed over the telephone as needed.

Medical History

A complete medical history will be obtained from the EHR at the Screening Visit (Day 0) and any changes (i.e., adverse events) from the Baseline visit (Day 1) will be documented at every visit thereafter. The information will be recorded on the REDCap eCRF.

Physical Examination

A complete physical examination will not be performed if there is a documented physical examination by a physician or nurse practitioner provider in the EHR within 24 hours prior to consenting. The findings of the examination will be recorded on the eCRF and serve as baseline findings.

Vital Signs

Temperature, heart rate, oxygen saturation, respiratory rate including respiratory parameters, and blood pressure will be obtained at the screening visit and during every visit from the EHR. The results will be recorded on the REDCap eCRF.
Review of Concomitant Medications

All concomitant medications and treatments will be captured at the Baseline and all subsequent visits in the REDCap eCRF. These data collection will include routine medications on admission, inhospital standard of care treatment, concomitant medications for th management of comorbidities, any prophylactic medications, dietary or nutritional supplements, and over-the-counter medications. In addition, EHR will be reviewed on daily basis to update REDCap eCRF to capture changes in standard of care and clinical management for COVID-19 in a dynamic landscape. Study team will inquire and record any home medications 7 days prior to enrollment. At the Screening visit, concomitant medication list will be solicited from the participant or LAR.

For the baseline visit, treatment intervention, and the follow-up visits, the following assessments will be completed:

Baseline variable collections:

- Presence or absence of inclusion and exclusion criteria
- Date and time of admission
- Demographics (age, sex, race, and ethnicity)
- Vitals and respiratory parameters
- Physical examination
- Comorbidities
- Acute signs and symptoms
- Parameters to assess severity-of-disease using the Acute Physiologic and Chronic Health Evaluation (APACHE) II classification, as applicable
- Current use of home and inhospital medications including over-the-counter
- Receipt of open label study medication
- Receipt of invasive procedures
- Blood and urine collections and analyses (see Table 4)
- Other procedures as per the Schedule of Events (see Section 1.3 Table 1)

Study intervention period (daily):

- Date and time of randomization
- Drug administration and accountability
- Vitals and respiratory parameters
- Physical examination
- Comorbidities
- Acute signs and symptoms
- Review of current medications
- Receipt of invasive procedures
- Hospital data including adverse events, endpoints, and outcomes

Nicotinamide Riboside for AKI in COVID-19 positive inpatients Protocol #: Not yet assigned

- Collect hospital data to complete APACHE-II
- Blood and urine collections and analyses (see Table 4)
- Other procedures as per the Schedule of Events (see Section 1.3 Table 1)

Assessments following Hospital Discharge: Early discharge (before completing 10-day intervention) and Follow-up visits

Early discharge: Using daily phone call or videoconferencing, following data will be collected

- Drug accountability
- Vitals and respiratory parameters
- Comorbidities
- Acute symptoms
- Review current medications
- Query about adverse events, endpoints, and outcomes
- Review EHR for additional data, if applicable
- Fingerstick blood creatinine using the POC device will be performed by the participant/care provider until Day 10 (see Table 4)
- Daily urine collections for biorepository (see Table 4)
- Blood collection will be done on Day 10 for research laboratory analysis and biorepository (see Table 4)
- Other procedures as per the Schedule of Events (see Section 1.3 Table 1)

Assessments for participants with early hospital discharge

It is reasonable to expect that a percentage of participants may be discharged home prior to completing 10-day in hospital intervention. In the event that participants will be discharged prior to the 10-day study intervention days of study drug administration, the study drug will be provided to participants in a pill box with written and verbal instructions to take twice daily for the remaining days to complete a 10-day course. To monitor compliance, at the time of discharge each participant will receive study drug administration and accountability log with instructions.

In addition, to monitor pattern of fingerstick creatinine, each participant will be provided with a StatSensor Xpress®, a home fingerstick point of care (POC) device for fingerstick creatinine measurement. The device is similar to a glucose meter that utilizes a test strip and a small drop of blood from finger stick. Participant and accompanying family member will receive a demonstration on how to use this device at the time of discharge along with lancets, alcohol swabs, test strips, and safe disposal biohazard waste containers. Using all safety measures, the study team will use the POC device using participant's fingerstick blood. The POC device generated fingerstick creatinine value will be documented and compared with the discharge day routine serum creatinine value. Participants will use POC fingerstick creatinine device daily for

the duration of the 10-day intervention period. Participants will receive daily virtual visit from the study staff to collect health status, provide study drug reminder and compliance, and collect POC device result. There will be a home visit at Day 10 to collect urine and blood in compliance with all local and applicable COVID-19 safety measures.

Follow up visits: At each follow-up visit (Day 30 and Day 90), the following assessments may occur at clinic or at home or by phone or videoconferencing and procedures will vary:

- Review of current medications
- Comorbidities
- Record vital signs and physical examination
- Collect data on adverse events, endpoints, and outcomes
- Collect blood and urine for research laboratory analyses and biorepository (see Table 4)
- Other procedures as per the Schedule of Events (see Section 1.3 Table 1)

Biospecimens Collections and Measurements

Primary and secondary endpoints from routine daily laboratory tests and clinical care:

Daily serum creatinine: Blood will be collected daily for the measurement of serum creatinine and documented for the study starting Day 1 and up to 10 days of hospitalization for participants who remain hospitalized or via StatSensor Xpress[®] for creatinine and outpatient serum creatinine measurement for participants who will be discharged prior to the 10-day intervention period. There will be a serum creatinine measured on the 10th day for discharged participants, in addition to the StatSensor Xpress[®] fingerstick creatinine measurement. AUC will be computed cumulatively across days for each patient.

Daily urine output: Daily urine output will be reported as part of routine clinical care and documented for the study starting Day 1 and up to 10 days of hospitalization. Daily urine outputs will not be obtained for participants who will be discharged prior to 10-day intervention period.

Onset of dialysis: Timing of onset of dialysis will be reported as part of routine clinical care and documented for the study starting Day 1 and up to 10 days of hospitalization.

Research Laboratory Biospecimens Collections for future Biomarkers Analysis:

Blood and urine will be collected at Visit 1 and then every visit thereafter for secondary or substudy analyses. Baseline (Day 1) blood and urine collections will be performed before participants receive first study drug dosing and after obtaining consent. There will be additional blood and urine collections on Day 1 at hour 3 and hour 6 after first drug administration for pharmacokinetics and analyses of biomarkers. Day 1 to Day 10 blood and urine collections will coincide with routine collection by the hospital staff. Hospital laboratory will aliquot and store the specimens and they will be picked up by the study team for storage in a COVID-19 designated biorepository. Each day, participants will collect first morning void urine into a provided container which will be kept refrigerated and picked up daily (until Day 9) by the courier service for delivery to the hospital laboratory. At Day 10, the study team will visit the participant at home to collect blood and first morning void urine and will deliver to the hospital laboratory. Both blood and urine biospecimens will be aliquoted and stored at the hospital laboratory by the hospital staff and will be picked up by the study team for storage in the COVID-19 designated biorepository at UTHSA. The list of research laboratory tests is provided in Table 4.

Blood and urine collections on Day 30 ± 3 and Day 90 ± 3 will take place when participants return to clinic or when the study team visits participants at home for follow-up visits. Collection, handling, and processing of all biospecimens will be performed in Biosafety Laboratory (BSL) 2 environment as per current US Centers for Disease Control and Prevention (CDC) guidance. Blood and urine biospecimens for analysis of biomarkers will be shipped to UTHSA and stored in a COVID-19 designated biorepository.

All blood and urine biospecimens will be tracked in the REDCap study database. Biosamples will be reconciled with the study schedule of events to assure that all expected biosamples are accounted for. Study biosamples in the UTHSA COVID-19 designated biorepository will retain association with the clinical data.

All assessments will be detailed in the MOP.

8.2 SAFETY AND OTHER ASSESSMENTS

Assuring participant safety is an essential component of this protocol. NR is considered GRAS (Generally Recognized as Safe) as filed for designation to FDA. Use of NR for the prevention and or treatment of AKI in COVID-19 positive participants, however, raises unique safety considerations. This protocol addresses these considerations through:

- Exclusion criteria designed to prevent potential overdose effects by excluding participants with concomitant intakes of niacin, nicotinamide, and NR;
- Daily assessment of participants health status;
- Systematic collection of safety outcomes;
- Structured reporting of adverse events;
- Appointment of independent safety adjudication committee (SAC)

Study procedures and evaluations to be done as part of the study to monitor safety and support the understanding of the study intervention's safety. For all visits starting from baseline until the last follow-up visits, the following assessments will be completed:

- Physical examination: A physical examination at the baseline visit or a record of routine physical examination performed within 24 hours prior to consenting, and at Day 30, and Day 90 follow-up visits.
- During the 10-day intervention period, participant's health status will be obtained on a daily basis from the participant and from EHR. Health status of participants will be collected by the study team at Day 30, and Day 90 follow-up visits. Participants will be specifically asked for any new symptoms on a daily basis.
- The safety clinical laboratory parameters will be performed at each visit while hospitalized. Any laboratory tests performed as part of routine clinical care (Clinical Laboratory Tests) within the specified visit window will be used for safety laboratory testing (see Table 4).

Research laboratory tests:

Blood for the first whole blood NAD+ level will be drawn within 6 hours prior to the first study drug dosing (i.e., baseline NAD+ level, Day 1). Whole blood NAD+ level will be measured daily for a total of 10 days while hospitalized starting at the baseline.

Safety laboratory from routine daily laboratory tests:

Safety laboratory will be performed at Visit 1 and then every visit thereafter for hospitalized participants. Clinical laboratory tests performed as part of routine clinical care in the 24 hours prior to first study drug dose will be accepted for the baseline (Day 1) safety laboratory tests. Any clinical laboratory tests (see Table 4) performed as part of routine clinical care within the specified visit can be used for safety laboratory testing within the period of hospitalization up to 10 days prior to starting the study drug.

Rationale for specific safety laboratory tests:

Several case studies reported that COVID-19 patients may present with mild symptoms such as muscle weakness with elevated CPK and laboratory confirmation of rhabdomyolysis [75-77]. Although, the incidence of rhabdomyolysis in COVID-19 is not known, several case reports indicate an association between rhabdomyolysis and AKI in COVID-19 patients [78-80]. One study reported elevated levels of CPK in about 14% of patients [21], suggesting involvement of muscle injury.

NR has been evaluated on the development of aging-induced non-alcoholic fatty liver disease in mice [81]. It was found that AST (aspartate transaminase) level was significantly reduced by NR supplementation while the alanine transaminase (ALT) level decreased without significance compared to baseline [81]. One human study demonstrated that NR significantly reduced AST level at day 56 from baseline [8]. It is likely that COVID-19 patients will be receiving different medications for comorbidities and as per the FDA guidance [82], liver function tests will be performed as listed in the Table 4.

Research laboratory tests	Safety laboratory tests	Repository			
Daily during Study Day 1 to Study Day 10					
Blood (daily):	Blood:	Blood:			
1.Whole blood NAD+	1. CPK on day 5	 Future biomarkers 			
2. Serum creatinine	2. Liver function tests on day 5	 Genetic analysis 			
(performed if	3 . Daily CBC and platelets				
routine test is	(performed if routine test is	Urine:			
missed or not	missed or not available)	 Future biomarkers 			
available)					
		Note: additional collections at			
Urine (daily):		hour 3 and hour 6 post-			
1. Urinalysis		randomization study drug for			
2. Urine creatinine		PK analysis			
3. UACR and UPCR					
4. Urine glucose					
5. Lactate					
6. Urine phosphate					
7. Urine NAD+					
metabolome					
Day 30 and Day 90	E				
Blood:		Blood:			
1. Serum creatinine		• Future biomarkers			
2. Whole blood NAD+		• Genetic analysis			
3. Serum electrolytes					
(Na, Cl, K)		Urine:			
4. Bicarbonate		• Future biomarkers			
5. Calcium and					
phosphate					
6. Blood glucose					
7. CBC with platelets					
T T •					
Urine:					
1. Urinalysis					
2. Urine creatinine					
3. UACK and UPCK					
4. Urine glucose					
5. Lactate					
0. Urine phosphate					
/. Urine NAD+					
metabolome					

Table 4: Blood and urine tests for research laboratory, safety, and repository

Due to limited direct interactions with the participants, safety assessments will be performed by collection of EHR data, participant interviews, vital sign measurements, physical examination, and laboratory tests, including complete blood count and comprehensive metabolic panel, and diagnostic tests or procedures. Participants' reported symptoms or complaints recorded in the medical record will be reviewed and recorded in the appropriate eCRF. In addition, information will be solicited from the participants and designated staff physicians to supplement accurate and complete safety assessment.

Each participating investigator will have primary responsibility for the safety of the individual participants under his or her care. The investigators will determine daily if any adverse events occur during the period from enrollment through study intervention and will determine if such adverse events are reportable. Thereafter, adverse events will not be required to be reported unless the investigator feels the adverse event was related to the study drug or study procedures.

The site investigator will (i) provide a verbatim term (a diagnosis where possible) for detected and reportable AE, (ii) each AE will also be described in terms of duration (start and stop date), severity, association with the study product, action(s) taken, and outcome, (iii) classify and assign a grade to each detected and reportable adverse event using the CTCAE v. 5.0 classification system, and (iv) rate the likelihood that the event was related to the study drug.

A team of medical monitors (Safety Adjudication Committee, SAC), composed of three clinicians with expertise in infectious disease or acute care management, one from each study site, independent of the study investigators will review the medical charts for unexpected AE /SAE data weekly during the study intervention period. The senior SAC member will serve as SAC Chair. The SAC will confirm the verbatim term (a diagnosis where possible) for detected and reportable adverse event with knowledge of the study site physician's rating and then classify and assign a grade to each detected and reportable adverse event using the CTCAE v. 5.0 classification system. Disagreements between the study site investigator and the SAC member will be adjudicated weekly on a call facilitated by the SAC Chair.

All AEs will be recorded on the AE eCRF. Verbatim terms for AEs will be coded to the current version of the MedDRA coding dictionary at the DCC. Verbatim terms will be coded at the Lower Level Term (LLT) where possible and to the Preferred Term (PT) otherwise. Accurate mapping to CTCAE will be confirmed during the coding review process. AEs and SAEs will be aggregated and reported for the DSMB at the PT level. If the SAC identifies an unexpected SAE, sIRB and FDA expedited reporting procedures will be followed and the DSMB will be notified.

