1 PROTOCOL SUMMARY

1.1 SYNOPSIS

Title	NIcotinamide Riboside in SARS-CoV-2 pAtients for reNAl protection (NIRVANA)			
Study Description	A pilot, double-blind, placebo-controlled, multicenter, interventional clinical trial with oral nicotinamide riboside (NR) 500 mg (versus placebo) twice daily for a total of 10 days in hospitalized participants with COVID-19.			
Objectives	Primary			
	 To determine the effect of nicotinamide riboside (NR) on whole blood NAD+ levels in hospitalized patients with COVID-19 infection and AKI during the 10-day intervention period; To evaluate the safety of NR in patients with COVID-19 infection and AKI during the 10-day intervention period; 			
	Secondary			
	 To determine the effect of NR on changes in area under curve (AUC) serum creatinine from baseline during the 10-day intervention; To determine the effects of NR on serum creatinine AUC, dialysis, and death with an ordinal categorical outcome having four categories (labeled 1, 2, 3, 4), defined as, in order from least to most severe disease, 1. Serum creatinine AUC < median, 2. Serum creatinine AUC ≥ median, 3. Dialysis, 4. Death during the 90d period post randomization; To determine the effect of NR on MAKE (Major Adverse Kidney Events; composite criteria defined as development or progression of chronic kidney disease, the initiation of long-term dialysis, or death from any cause) at 30d and 90d post randomization; To determine the effect of NR on degree of kidney impairment defined with estimated glomerular filtration rate (eGFR) and proteinuria at 30d and 90d post randomization; 			
	Exploratory			
	• To determine the relationship of whole blood NAD+ levels with AUC creatinine and surrogate markers of AKI such as kidney injury molecule- 1 (KIM-1) and neutrophil gelatinase-associated lipocalin (NGAL);			
Endpoints	Primary			
	 Rates of change in whole blood NAD+ level from baseline to day 10 in NR compared to Placebo. Safety of NR in hospitalized patients with COVID-19 and AKI (defined as the occurrence of at least one serious adverse event of grade 3 or higher or the occurrence of thrombocytopenia (>25% decline in blood platelet count from baseline value). 			

	Secondary				
	 Rates of change in AUC serum creatinine benchmarked to baseline from baseline to day 10 in NR compared to Placebo; An ordinal categorical outcome with four categories (labeled 1, 2, 3, 				

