3 OBJECTIVES AND ENDPOINTS

OBJECTIVES	ENDPOINTS	JUSTIFICATION FOR		
		ENDPOINTS		
Primary				
 To determine the effect of nicotinamide riboside (NR) on whole blood NAD+ levels in hospitalized patients with COVID-19 infection and AKI during the 10-day intervention period; To evaluate the safety of NR in patients with COVID-19 infection and AKI during the 10-day intervention period. 	 The primary endpoint is the rate of change in whole blood NAD+ level over the 10 day period from baseline to day 10. Safety of NR in hospitalized patients with COVID-19 and AKI (defined as the occurrence of at least one serious adverse event of grade 3 or higher or the occurrence of thrombocytopenia defined as >25% decline in blood platelet count from baseline. 	 Recent clinical data indicate a reduction of blood NAD+ level in AKI patients and an increase in NAD+ in 48 hrs with NR treatment; The safety of NR in COVID-19 patients is not known 		
Secondary	-	-		
• To determine the effect of	• The rate of change in AUC	• The recovery of AKI, as		
NR on changes in AUC	benchmarked to baseline;	assessed by AUC serum		

Table 2: Study objectives, endpoints, and justification for endpoints

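### Between discharge and Day 10 the plan is unclear on whether platelets are counted, so falls that belong to the primary safety endpoint can be missed

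*Combined protocol and SAP*

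**What the plan says.** The synopsis sets the safety objective as "To evaluate the safety of NR in patients with COVID-19 infection and AKI during the 10-day intervention period". One component of the endpoint, in section 3, is "the occurrence of thrombocytopenia defined as >25% decline in blood platelet count from baseline"; the synopsis gives the same threshold.

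On when platelets are measured, the plan says different things in different places:

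- **Section 8.2, text.** "The safety clinical laboratory parameters will be performed at each visit while hospitalized", and again, under the safety laboratory paragraph, "Safety laboratory will be performed at Visit 1 and then every visit thereafter for hospitalized participants". Both limit the tests to inpatients.
- **Table 4 (section 8.2).** The safety column for Days 1 to 10 lists "Daily CBC and platelets", to be done by the study if the routine test is missing. It carries no inpatient limit. At Day 30 and Day 90 the table lists "7. CBC with platelets".
- **Table 1 (section 1.3).** Safety blood analysis is marked for Days 1 to 10, 30 and 90, whether or not the participant has gone home.
- **Sections 6.1.1 and 8.1, participants discharged early.** The blood tests named are a daily fingerstick creatinine and one home draw: "Blood collection will be done on Day 10 for research laboratory analysis and biorepository". In Table 4, platelets for Days 1 to 10 are in the safety column, not the research column.

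Section 8.1 expects that some participants will leave hospital before Day 10. They take the remaining study drug at home.

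**The concern.** The platelet component is met if a qualifying fall is ever recorded. Such an endpoint can only be met on days when someone counts platelets. If counting stops at discharge, the chance of recording a fall depends on length of stay, which is settled after randomization and could be affected by treatment.

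The other follow-up does not fill the gap. Daily calls cannot detect a fall in count that causes no symptoms. Day 30 and Day 90 counts lie outside the 10-day window and can miss a fall that has recovered; section 2.3.1 describes the thrombocytopenia reported with nicotinamide in hemodialysis patients as transient. Section 9.4.2 plans Fisher's exact test on participants with at least one event and makes no allowance for time under observation. Section 9.4.1 offers multiple imputation in general terms, but no rule says how to classify a participant who has no count after discharge.

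The result matters beyond this trial. All three scenarios for later studies in section 2.1 require no significant increase in harm. Platelets are also a named concern: section 2.3.1 reports a statistically significant decrease with NR in healthy volunteers.

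**Working it through.** **Plan's own figure.** The plan states no event rate, discharge rate or power for the safety endpoint. The power statement in section 9.2 concerns NAD+ only and has no bearing here. Everything below therefore rests on assumed rates.

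**Inputs from the plan.** Threshold of more than 25% below baseline (section 3); baseline on Day 1, leaving nine possible daily counts on Days 2 to 10 (Table 1); 100 participants randomized 1:1, so 50 per arm (sections 5.5 and 6.1.1); two-sided Fisher's exact test at 5% (section 9.4.2).

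**Assumptions.** A constant daily chance q of a first qualifying fall, the same in both arms and the same at home as in hospital; 5 post-baseline test days for a participant discharged early and 9 for one who stays; no count after discharge, including on Day 10.

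**Step 1: chance of a recorded fall with k test days, 1 − (1 − q)^k.**

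| q per day | k = 5 | k = 9 | Difference |
|---|---|---|---|
| 2% | 9.6% | 16.6% | 7.0 points |
| 3% | 14.1% | 24.0% | 9.9 points |
| 5% | 22.6% | 37.0% | 14.4 points |

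The last column is the gap between arms only if everyone in one arm leaves early and nobody in the other does.

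**Step 2: gap between arms when only some leave early.** This is the difference in the share discharged early, times the difference from step 1.

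| q per day | 50% v 30% early (× 0.2) | 70% v 30% early (× 0.4) | Equal shares (× 0) |
|---|---|---|---|
| 2% | 1.4 points | 2.8 points | 0 |
| 3% | 2.0 points | 3.9 points | 0 |
| 5% | 2.9 points | 5.7 points | 0 |

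**Step 3: a second parameterization.** Fix the true 10-day rate, spread it at constant hazard over Days 2 to 10, and let early leavers have their last count on Day 4 or 5. With 30% discharged early in one arm and 50% to 70% in the other, and no true difference, the arm discharged earlier shows a rate lower by 1 to 3 points (true rate 10%), 2 to 5 (20%), 3 to 8 (30%) or 4 to 10 (40%).

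**Step 4: loss of sensitivity to real harm.** Take the same model with last count on Day 5, true platelet rates of 40% on NR and 20% on placebo, and 50 per arm. The recorded rate is p × (1 − f) + f × [1 − (1 − p)^(4/9)], where f is the share discharged early.

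| Early discharge, NR v placebo | Recorded rates | Fisher power to detect harm |
|---|---|---|
| Counts complete to Day 10 | 40.0% v 20.0% | 52% |
| 50% v 50% | 30.2% v 14.7% | 37% |
| 50% v 30% | 30.2% v 16.8% | 27% |

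The middle row shows that power is lost even when discharge timing is the same in both arms.

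**Step 5: effect of a Day 10 count.** If a count on the home sample caught half of the falls that occurred after discharge, each gap in step 3 would halve. Only counts through Day 10 in everyone would bring it to zero.

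**The case against.** A Day 10 home count may already be intended. Section 6.1.1 explains that home visit as serving the primary outcome, and safety is a primary endpoint. The early-discharge list in section 8.1 ends by referring to Table 1, which marks safety bloods on Day 10. Section 8.1 also defers detail to the manual of operations, which is not among these documents. This stands: a Day 10 count is unclear, not excluded. It does not remove the conflict with the two statements in section 8.2, and one count would not cover the days between discharge and Day 10.

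A reader might infer that platelets are followed only in hospital. The documents do not support that, because Table 4 has counts at Day 30 and Day 90. A reader might also take 14% versus 24% as the expected distortion. That contrast needs early discharge in 100% of one arm and 0% of the other.

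The bias between arms is conditional. Nothing in the documents shows that NR changes length of stay. The model also gives people well enough to go home the same daily risk as those still in hospital, which probably overstates what is missed. Only the platelet component is affected: adverse events are still sought after discharge by daily contact and record review, and a participant who already has a qualifying serious event counts on the composite anyway. These points limit the size; they do not answer the loss of sensitivity.

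**Conclusion.** The concern holds for the interval from discharge to Day 10. The text of section 8.2 and Tables 1 and 4 give conflicting instructions on platelet counts, and sites following the text would under-record one component of the primary safety endpoint among participants still taking study drug at home. Both arms' rates would be understated and power to detect harm reduced; the comparison would be biased only if discharge timing differed by arm.

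At an assumed 3% daily chance, with 5 versus 9 test days, the gap is about 2 points for early discharge of 50% versus 30% and about 4 points for 70% versus 30%. With equal timing it is nil under the null. These sizes rest on assumed rates, a constant hazard and no Day 10 count. The documents do not support a claim that the platelet comparison will be biased in a known direction.

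**What to change.** 1. Reconcile the safety laboratory statements in section 8.2 and the early-discharge list in section 8.1 with Tables 1 and 4, so that one rule states which platelet counts are made after discharge and up to Day 10.
2. Run a platelet count on the Day 10 home sample. Section 6.1.1 already has it drawn by a phlebotomist and delivered to the hospital laboratory.
3. State how participants without counts through Day 10 are classified on the endpoint.
4. Add a sensitivity analysis of Day 10 against baseline platelets in participants who are alive and have a Day 10 sample. It cannot include those who die earlier or have no sample, so report their numbers by arm beside it.
5. Tabulate the number of platelet tests per participant by arm, so that unequal observation is visible.

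The cost is one extra assay per discharged participant on blood already being drawn, plus a short text amendment and two tables. The gap is narrowed, not closed: a fall that recovers before Day 10 would still go unrecorded.
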